10.6 PRIMARY SAFETY ANALYSIS

10.6.1 The Primary Safety Hypothesis

The primary safety research hypothesis to be tested is that the rate of Major Adverse Events (MAEs) at 30 days in the test group is less than the rate of MAE at 30 days in the control group. The null and alternative hypotheses are provided below.

$$H_0: P_t \geq P_c \quad \text{vs.} \quad H_1: P_t < P_c, \quad \text{where:}$$

P_t is the MAE rate at 30 days in the test group;

P_c is the MAE rate at 30 days in the historical surgical control group.

10.6.2 Sample Size

The primary trial safety variable is the rate of MAEs (as previously defined) at 30 days following treatment with the Fenestrated Stent Graft System. In the U.S., the alternative for these patients with juxtarenal or pararenal aortic aneurysm is open surgical repair. The open surgical concurrent control group enrolled in the original Endologix trial between 2000 and 2003 (that served as the basis for approval of the bifurcated stent graft under P040002) consisted of patients with aneurysms of these types. Of the 66 control patients enrolled in that trial, 3.0% had a suprarenal aneurysm, 21% had a pararenal aneurysm, and the remaining patients (76%) had a juxtarenal aneurysm or infrarenal aneurysm unsuitable for endovascular repair with the Endologix bifurcated device. These patients have completed full five year follow-up as documented in the Endologix PMA final report approved by FDA in 2009 (P040002/R008).

Owing to the availability of patient-level data within the Endologix PMA P040002 for this historical surgical control group with more complex aneurysms as intended to be enrolled in this trial, it is reasonable to consider it for sample size generation for the safety endpoint. The MAE incidence at 30 days in the original PMA trial for the test group and this surgical control group is tabulated below:

¹⁷Fleiss, J. The statistical basis of meta-analysis. *Statistical Methods in Medical Research* 1993;2:121-45.

30-Day MAE Rates in the Endologix PMA Trial (P040002)

Event	Powerlink Test (N=192)	Surgical Control (N=66)
Patients with ≥ 1 MAE	16 (8.3%)	44 (67%)
All-Cause Mortality	2 (1.0%)	4 (6.1%)
Bowel Ischemia	0	6 (9.1%)
Myocardial Infarction	3 (1.5%)	5 (7.6%)
Paraplegia	0	0
Renal Failure	2 (1.0%)	6 (9.1%)
Respiratory Failure	2 (1.0%)	5 (7.6%)
Stroke	0	1 (1.5%)
Blood Loss $\geq 1,000$ cc	11 (5.7%)	38 (58%)

Thus, the 30-day MAE rates were 8.3% (endovascular test group) and 67% (surgical control group). To be conservative and to account for the fact that in the present trial, only more complex juxtarenal or pararenal aneurysms will be treated endovascularly, the rate for the test arm has been increased to 16.6%. It is expected that the rate of MAEs within 30 days in the treatment group in this trial will be smaller than that of the historical surgical control group as noted above. The sample size for this trial is calculated by considering this a superiority trial.

The primary hypothesis to be tested in this analysis is the following:

$$H_0: P_t \geq P_c \quad \text{vs.} \quad H_1: P_t < P_c, \quad \text{where}$$

P_t is the MAE rate at 30 days in the test group;

P_c is the MAE rate at 30 days in the historical surgical control group.

If we assume that $P_t = 0.166$, $P_c = 0.670$, one-sided alpha = 0.025, and power = 80%, a very small number of patients (<10) are required in the treatment group to test the above hypothesis, given 66 patients in the control group. If there are 97 evaluable patients in the test arm, P_t would have to be 0.434 for there to be 81% power with an alpha of 0.025.

10.6.3 Propensity Score Analysis

Because it is expected that there will be differences between the treated and control patients that might bias the comparison, a propensity score analysis will be attempted. This analysis will be done by an independent statistician (i.e., not affiliated with Endologix or with the primary study statistician, [name] and Associates) without knowledge of the primary safety outcomes that are adjudicated by the independent Clinical Events Committee. Furthermore, this analysis can be performed after all test patients are enrolled, and before the endpoint is reached by all patients. The independent statistician will be required to document

in his or her report the data and documentation received from the data management group for the control and test patients, with clear acknowledgement that no MAE outcomes data were provided or were available in any way.

A non-parsimonious logistic regression analysis modeling treatment assignment by baseline covariates will be done initially. Covariates for this analysis will be age, gender, ASA class, cardiac/coronary artery disease (a composite variable to include arrhythmia, CHF, prior MI, CABG/PCI, heart valve repair/replacement), histories of cancer, cerebrovascular disease, coagulopathy, COPD, diabetes, hypertension, liver disease, peripheral arterial occlusive disease, renal failure, smoking history, and aneurysm diameter. For the propensity score analysis, in covariates where missing data occurs, the missing data will be imputed by using the median by treatment group for the missing value unless the number of patients with missing data is large (greater than 10% of the sample size). In that case, the missing value will be imputed by one of two methods. If the variable is quantitative, the following steps will complete the imputation (stratified hot deck imputation):

1. A histogram will be computed;
2. A uniform random number between 0 and 1 will be chosen and compared to the relative frequency of the bars in the histogram to determine the range of the value.
3. A second uniform random number will be generated, multiplied by the range for the bar selected above; the integer portion of this product will be added to lower limit of the range to obtain the imputed value.

If the variable is categorical, the correlation of the cases with other covariates will be evaluated to determine if there is a relationship between the value of the variable with missing data and a function of other covariates used in the analysis that results in ordinal integer values (perhaps the sum of a subset of several covariates that are present could be used). If there is a significant correlation between the variable with missing values and the function, a cross tabulation of the subjects with scores for the variable with missing data and the function values will be formed. The value of the missing observation will be assigned by generating a uniform random number and comparing that random number to the relative marginal frequency of the distribution of observed values for the given score of the function. If no function can be found to be correlated with the data, the values will be assigned by simple random selection with replacement from subjects with values within treatment groups.

The model will be obtained by including all covariates in the model. The final propensity model will contain all covariates for the first evaluation of balance. The propensity score analysis will be done without knowledge of MAE results for the test group. This is made possible by the fact that test group MAEs are determined by an independent Clinical Events Committee; their adjudicated results are not part of the clinical database but are separately maintained in a dedicated CEC database.

The data will be divided into quintiles. Within the quintiles, the baseline characteristics are evaluated by comparing each characteristic between the test and control groups and observed to determine if a characteristic for which a statistically significant difference was observed

without adjustment is no longer statistically significant. An analysis of balance will be done by the method recommended by Rosenbaum and Rubin.¹⁸ For each continuous or ordinal covariate, an analysis of variance with two treatment groups and five stratum class variables will be done. An examination of the F-tests across and within strata will be examined.

Significant main effect or interactions from this analysis will be evidence of imbalance. For categorical covariates, this analysis will be done with logistic regression. With the logistic regression analyses, the output Chi-square values will be examined. The maneuvers to be attempted if adequate balance is not achieved by the initial propensity model include reducing the model by removing non-significant covariates and adding higher order terms for significant covariates to the propensity model to see if the resulting propensity score assignments improve the balance. After each propensity adjustment, the same balance analyses will be done.

If an adequate degree of adjustment cannot be achieved using quintiles because of sparse representation of the test or control groups in a given stratum (less than two patients to allow estimation of the variance for continuous or ordinal covariates), the analysis will be attempted by using quartiles. If the data are still too sparse, tertiles will be used. While dividing the data into quintiles accounts for about 90% of the bias in measured variables, quartiles accounts for about 85% bias reduction, and tertiles account for about 80% bias reduction.^{19,20}

The sole rationale for acceptability of the degree of adjustment will be based on the F-statistics for continuous or ordinal covariates or the chi-square statistics for categorical covariates.¹⁷

If significant imbalance remains, the analysis involving the control group will be abandoned and an alternative analysis of the performance goal discussed in §10.6.4 will be used as the primary safety analysis.

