5.2. PATIENT INCLUSION CRITERIA

A patient who meets *all of the following criteria* potentially *may be included* in the study:

- (a) Male or female at least 18 years old;
- (b) Informed consent form understood and signed and patient agrees to all follow-up visits;
- (c) Have abdominal aortic aneurysm with diameter ≥ 5.5 cm, or between 4.5 and 5.5cm and rapidly expanding (>0.5 cm in six months), or $>50\%$ larger than the normal aortic diameter;
- (d) Anatomically eligible for the Bifurcated System and for the Fenestrated Stent Graft System per the indications for use (IFU):
 - 1) Adequate ipsilateral iliac/femoral access compatible with the required delivery systems (diameter ≥ 8 mm)
 - 2) Non-aneurysmal infrarenal aortic neck <15 mm in length;
 - 3) Most caudal renal artery to the aortoiliac bifurcation length ≥ 70 mm;
 - 4) SMA to aortoiliac bifurcation length ≥ 90 mm;
 - 5) Infra-SMA non-aneurysmal[†] aortic neck diameter 18 to 34 mm;
 - 6) Infra-SMA non-aneurysmal aortic neck length ≥ 15 mm;
 - 7) Infra-SMA non-aneurysmal aortic neck angle $\leq 60^\circ$ to the aneurysm sac;
 - 8) Angle $\leq 60^\circ$ (clock face) between the SMA and CA;
 - 9) Renal arteries both distal to the SMA by ≤ 35 mm;
 - 10) Renal arteries axially within ≤ 30 mm of each other
 - 11) Renal arteries both with luminal diameter of 4 to 8mm;
 - 12) Renal arteries with an angle (clock face) of 90° to 210° to each other;
 - 13) Common iliac artery distal fixation sites length ≥ 15 mm;
 - 14) Common iliac artery distal fixation sites angle to the aortic bifurcation $\leq 90^\circ$;
 - 15) Ability to preserve at least one hypogastric artery;
 - 16) The Endologix Fenestrated Proximal Extension Stent must have the ability to overlap the bifurcated stent graft by at least 3cm.
 - 17) Aortic diameter at the most caudal renal artery of 18 to 36mm

[†]Non-aneurysmal is defined as $<20\%$ diameter change over a length of at least 15mm below the SMA.

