To determine those factors that may be associated with MAE, a supportive covariate analyses will be performed by logistic regression to determine if there are differences in the rates among groups when adjusted for other factors. Covariates for these analyses will be age, gender, ASA class, cardiac/coronary artery disease (a composite variable to include arrhythmia, CHF, prior MI, CABG/PCI, heart valve repair/replacement), histories of cancer, cerebrovascular disease, coagulopathy, COPD, diabetes, hypertension, liver disease, peripheral arterial occlusive disease, renal failure, smoking, selected aneurysm characteristics, propensity class (numerical classification of the stratum based on patient's propensity score), plus any variables found to be out of balance in the comparability analyses. Because there is no exact congruence of study sites between the test and control groups it is not possible to account for study site in this analysis. To observe the effect of study site, a multivariable analysis will be done only in the test patients to determine if the study site remains a significant influence to the rate of MAE when other covariates are included in the analysis. Often the differences in study site responses are the result of differences in baseline characteristics the patients at that site such that when a model includes both the study site effect and the covariates effect, the study site no longer retains statistical significance.

If it is not possible to break the data into classes that provide adequate coverage of both treatment groups in each stratum, an alternative primary safety test will be done against a performance goal of 56% derived from the Society for Vascular Surgery (SVS) major adverse

events outcomes for infrarenal open surgical control patients.²² This is reasonably conservative as a performance goal. To this point, a recent publication finds that the rates of these major adverse events are similar between open infrarenal aneurysm repair and open complex aneurysm repair (juxtarenal, pararenal, suprarenal), with the exception of bleeding and renal events, which were significantly higher with open complex aneurysm repair.²³

The null and alternative hypotheses are provided below.

$$H_0: P_t \geq 0.56$$

versus

$$H_1: P_t < 0.56$$

where P_t is the MAE rate at 30 days in the test group

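### The propensity model for the primary safety comparison leaves out aneurysm location, a potential confounder of unknown direction and size

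*Combined protocol and SAP*

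**What the plan says.** - **Propensity covariates (Section 10.6.3).** The list covers age, gender, ASA class, cardiac disease and comorbid histories, and closes with "liver disease, peripheral arterial occlusive disease, renal failure, smoking history, and aneurysm diameter". It has no item for location, extent or neck. If balance is poor, the plan may drop non-significant covariates or add higher-order terms for significant ones. Neither step brings in a new variable. If significant imbalance remains, the primary analysis switches to the performance goal.
- **Primary test (Section 10.6.4).** Differences in MAE proportions are combined over the propensity strata, with a further adjustment for site if sites differ. Nothing else is adjusted for.
- **Control anatomy (Section 10.6.2).** Of the 66 controls, "3.0% had a suprarenal aneurysm, 21% had a pararenal aneurysm, and the remaining patients (76%) had a juxtarenal aneurysm or infrarenal aneurysm". The infrarenal cases in that last group are described as unsuitable for the sponsor's bifurcated device.
- **Test anatomy.** Section 10.6.2 says that in this trial "only more complex juxtarenal or pararenal aneurysms will be treated endovascularly". Section 5.2 requires "Non-aneurysmal infrarenal aortic neck <15 mm in length".
- **Location as a prognostic factor (Section 10.6.4).** To support the 56% goal, the plan cites a publication that found similar event rates in infrarenal and complex open repair, "with the exception of bleeding and renal events, which were significantly higher with open complex aneurysm repair".
- **Supportive model (Section 10.6.4).** A logistic regression for MAE includes aneurysm features that are not named.

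**The concern.** The plan expects the treated and control groups to differ and relies on the propensity score to remove the resulting bias. Blood loss and renal failure are both MAE components, and by the plan's own citation both vary with the complexity of open repair. Blood loss is also the dominant control event: 38 controls had it, and 44 had any MAE. Strata balanced on comorbidity and diameter can therefore still compare patients with different anatomy.

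The balance check does not close the gap. Section 10.6.3 compares baseline characteristics within strata without listing them, so an imbalance in location need not be noticed and need not trigger the 56% fallback. The comparability analysis in Section 10.4 is between trial sites, not between test and control. What is at stake is the size of the reported advantage over open surgery and, at test MAE rates far above the planned one, the decision itself.

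**Working it through.** **1. The plan's own figure.** For 97 test and 66 control patients and a control rate of 0.670, Section 10.6.2 says "P_t would have to be 0.434 for there to be 81% power with an alpha of 0.025". Enumerating the one-sided Fisher exact test gives 0.810, so the 81% reproduces. The omission does not make the power statement wrong.

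**2. Control counts by location (Section 10.6.2).** 0.030 × 66 = 1.98, so 2 suprarenal. 0.21 × 66 = 13.86, so 14 pararenal. 0.76 × 66 = 50.16, so 50 juxtarenal or infrarenal. The split of the 50 is not given. The crude MAE rate is 44/66 = 66.7%.

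**3. Location-matched control rate.** The documents give no MAE rate by location. Assume a rate *a* in the 16 pararenal or suprarenal controls. The other 50 then have *b* = (44 − 16*a*)/50. For a test group with pararenal share *q*, the matched control rate is *qa* + (1 − *q*)*b*.

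| *a* (assumed) | *b* | *q* = 10% | *q* = 50% |
|---|---|---|---|
| 66.7% (equal rates) | 66.7% | 66.7% | 66.7% |
| 75% (12/16) | 32/50 = 64% | 0.075 + 0.576 = 65.1% | 0.375 + 0.320 = 69.5% |
| 100% (16/16) | 28/50 = 56% | 0.100 + 0.504 = 60.4% | 0.500 + 0.280 = 78.0% |

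The shift runs from about −6 to +11 percentage points and is zero under equal rates.

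**4. The suprarenal controls alone.** Without these two, the control rate is 42/64 = 65.6% if both had an MAE and 44/64 = 68.8% if neither did.

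**5. The infrarenal controls alone.** Suppose they had the 56% rate of the performance goal. Removing *k* of them gives (44 − 0.56*k*)/(66 − *k*): 68.6% for *k* = 10, 71.3% for 20 and 75.6% for 30. This moves the control rate up, so their presence would work against the device.

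**6. Effect on the decision.** This step uses a crude one-sided Fisher test at 0.025 as a stand-in for the stratified test. The largest number of test MAEs that still passes is:

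- 48/97 (49.5%) against all controls, 44/66;
- 47/97 or 50/97 against 42/64 or 44/64;
- 36/97 (37.1%) against 28/50, which is the extreme case of *a* = 100% and no pararenal test patients.

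The planned rate is 16.6%, or about 16/97. Even against 28/50, power at that rate is 99.9% (pooled normal). A pass could become a fail only at test rates of roughly 35% to 50%. If the test group were rich in pararenal cases, the limit would instead rise above 49.5%.

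**The case against.** The strongest reply is that nothing shows the two groups to differ on location in a way that matters. The juxtarenal/pararenal mix of the test group is not known in advance. The cited publication contrasts infrarenal with complex open repair, puts juxtarenal on the complex side, and does not say that pararenal differs from juxtarenal. It makes location prognostic for open repair only. Section 4.2 treats juxtarenal aneurysm as a subset of infrarenal, and Section 5.2 admits short infrarenal necks, so some infrarenal controls may resemble trial patients. The supportive regression also offers a place to look at location. All of this stands, and it is why location should be called a potential confounder and no more. An undefined term in a supportive model does not repair the primary analysis, however.

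A reader might infer that the omission favours the device. The documents do not support that: suprarenal controls, or a higher pararenal share among controls than in the test group, could favour it, while lower-risk infrarenal controls would work against it. A reader might also infer a serious loss of type I error control. With no device effect within location and no pararenal test patients, the crude rejection rate (pooled normal) is about 5%, 11% and 27% for *a* = 75%, 85% and 100%, against 2.5%. Those figures need a test group without cases that the trial enrols, and the highest also needs an MAE in every one of the 16 controls.

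**Conclusion.** The point holds as a gap in the primary adjustment. Location is plausibly prognostic by the plan's own citation, the control anatomy is mixed, and neither the propensity score nor its balance check is required to consider it. Direction and size are unknown. Under the stated assumptions (75% to 100% MAE in the 16 pararenal or suprarenal controls, 10% or 50% pararenal in the test group), the matched control rate lies between about 60% and 78%, against 67% crude.

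The documents do not support reading this as a threat to the planned conclusion: at 16.6% the trial passes in every scenario considered, and the 81% power figure is sound. The exposure is to the reported adjusted difference, and to the decision only if the test MAE rate were two to three times the planned one. The decision limits come from an unstratified test and are indicative.

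**What to change.** Before the outcome-blind propensity step:

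1. Add location, coded as pararenal versus juxtarenal or short-neck, to the covariate list in Section 10.6.3, and name it in the balance check there.
2. Add a sensitivity analysis of the primary safety comparison restricted to controls with trial-eligible anatomy. This excludes the roughly 2 suprarenal controls and, where the control records allow, infrarenal controls that do not meet the short-neck criterion. A propensity term cannot adjust for locations that the test group does not contain, so the first step alone is not enough.

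This is a cheap improvement. Test anatomy is already assessed from the baseline CT (Sections 8.6.2 and 11.1), and Section 10.6.2 says patient-level control data are available. Because the propensity work is done without MAE results, the covariate can be added without outcome-driven selection. The costs are slightly sparser strata, one more variable whose imbalance could send the analysis to the 56% goal, and a smaller control group in the sensitivity analysis. Whether the control records separate juxtarenal from infrarenal cases is not shown, because Section 10.6.2 reports them as one group. That should be checked first.

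### Whether the surgical control stays in the primary safety test is decided only by significance tests on 15 covariates, which barely respond to how different the groups are

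*Combined protocol and SAP*

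**What the plan says.** Section 10.6.3 builds a logistic propensity model for group membership. The covariate list begins "Covariates for this analysis will be age, gender, ASA class, cardiac/coronary artery disease" and comes to 15 in all: age, gender, ASA class, the cardiac composite, ten comorbidity and smoking histories, and aneurysm diameter. The score is cut into quintiles, or into quartiles and then tertiles if strata are sparse.

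Balance is then tested one covariate at a time: "For each continuous or ordinal covariate, an analysis of variance with two treatment groups and five stratum class variables will be done". The section adds "An examination of the F-tests across and within strata will be examined", and for categorical covariates "With the logistic regression analyses, the output Chi-square values will be examined". The reading of the results is "Significant main effect or interactions from this analysis will be evidence of imbalance".

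The criterion is exclusive: "The sole rationale for acceptability of the degree of adjustment will be based on the F-statistics for continuous or ordinal covariates", or on the chi-square statistics for categorical covariates. If balance fails, the model is refitted, with higher-order terms as a second option, and the same tests are repeated: "The maneuvers to be attempted if adequate balance is not achieved by the initial propensity model include reducing the model by removing non-significant covariates". The end of the path is "If significant imbalance remains, the analysis involving the control group will be abandoned", after which the performance goal in section 10.6.4 becomes the primary safety analysis.

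Section 10.6.4 words the trigger for that 56% goal differently. There it applies when the data cannot be divided into classes that adequately cover both groups in every stratum.

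**The concern.** The rule selects the primary safety hypothesis: superiority to the sponsor's open surgical control (section 10.6.1) or an MAE rate below a fixed 56% (section 10.6.4). It should therefore respond to how different the groups are after adjustment. There are two reasons to doubt that it does.

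First, there are about 30 tests with no stated level and no allowance for their number, so some significant results are expected by chance. Second, the strata are built from a score fitted to the covariates being tested. That suppresses the main-effect tests and leaves the verdict to the interaction tests, which say little about the overall difference between groups.

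At stake are the comparative claim against open surgery and its credibility, in both directions: a usable control group may be dropped, or a poorly matched one accepted.

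**Working it through.** **Inputs from the plan.** 97 test and 66 control patients (section 10.6.2); 15 covariates, five strata, one main-effect and one interaction test per covariate (section 10.6.3); one-sided 0.025 for the MAE test; 56% goal (section 10.6.4).

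**Assumptions, because the plan is silent.** Each balance test at 0.05; one significant result counts as a flag; 3 continuous or ordinal and 12 binary covariates, with assumed prevalences; the refit sequence.

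**1. The plan's own figure.** The plan gives no error rate for the balance rule. The nearest figure is 81% power with 97 versus 66 patients at rates of 0.434 versus 0.670. A one-sided Fisher exact test, fully enumerated, gives 81.0%, so it is reproduced.

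**2. Independent tests.** P(at least one significant) = 1 − 0.95^m.
- m = 15: 1 − 0.95^15 = 53.7%
- m = 30: 1 − 0.95^30 = 78.5%

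**3. Effect of the fitted score.** With no true difference, random strata gave at least one significant main effect in 53.0% of data sets. Strata from the fitted score gave 1.3%. The per-test rate on the fitted score was 0.001 for main effects and 0.057 for likelihood-ratio interactions. About 15 tests are thus really in play: 1 − (1 − 0.057)^15 = 58.5%, against 59.0% simulated for any interaction.

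**4. Truly balanced data sets flagged.** The ranges span different assumed prevalences and, after refits, different refit sequences.

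| Form of test for binary covariates | First fit | After refits |
|---|---|---|
| Likelihood-ratio chi-square | 57% to 66% | 24% to 33% |
| Linear F | 48% to 50% | not run |
| Wald chi-square | 14% to 38% | about 6% |

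If two flagged covariates were needed instead of one, the first-fit rates were 25% to 28% (likelihood ratio) or 4% to 6% (Wald). A run of 200 data sets has a standard error of up to √(0.25/200) = 3.5 points.

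**5. Does the flag track imbalance?** First-fit flag rates as the true difference grows:

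| Series | 0 | 0.3 SD | 0.5 SD |
|---|---|---|---|
| Likelihood ratio, A | 66% | 68% | 64% |
| Likelihood ratio, B | 57% | 60% | 63% |
| Likelihood ratio, C | 62% | 64% | 53% |
| Wald | 23% | 22% | 17% |

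One series rises by 6 points; the other three end lower than they began. The median largest adjusted standardised difference hardly separates flagged from unflagged sets: 0.099 versus 0.097 with no difference (series B), and 0.145 versus 0.125 (series A) or 0.18 versus 0.18 (series B) at 0.3 SD. At 0.5 SD, between 39% and 70% of accepted sets still had a covariate above 0.25.

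**6. Cost of abandonment.** Exact binomial test against 0.56 with n = 97: reject at 44 or fewer events, since P(X ≤ 44 | 0.56) = 0.0227.
- At a true rate of 0.434, power is 69%, against 81% for the control comparison.
- At the planned 0.166, power is about 100%.

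**The case against.** A reader might infer that half to two thirds of well-balanced trials would lose their control comparison. The documents do not support that, for three reasons.

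- A first flag is not abandonment. Section 10.6.3 requires refits and repeat tests, and drops the control only if imbalance remains.
- The higher rates belong to likelihood-ratio or linear F-tests. The chi-square form is not stated. Section 10.3 defers to SAS defaults without naming a procedure, and Wald tests give much lower rates.
- The section calls a significant result evidence of imbalance and speaks of adequate balance. It does not say that a single result among about 30 decides.

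A reader might also infer that the rule lets the sponsor choose the easier test. It does not: the propensity work is done by an independent statistician without MAE outcomes, and the fallback goal is fixed in advance. Section 10.8.1 also keeps an adjusted comparison with the control if balance fails, although an exploratory one. The balance method follows a cited subclassification approach, and any numeric limit put in its place is a convention.

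These points stand, and they reduce the size and severity of the concern. They do not rescue the criterion. Under Wald tests too, the flag rate does not rise with the true difference, and blinding does not make an uninformative test informative. The unstated level, test form and tolerated number of significant results are themselves gaps in a rule that selects the primary analysis.

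**Conclusion.** The concern holds as a should-fix. The balance rule is underspecified and, on any reasonable completion, a poor measure of balance. With 0.05 per test and one result deciding, chance flags about 14% to 38% (Wald) or 48% to 66% (likelihood ratio or linear F) of balanced data sets at the first fit. About 6% to 33% stay flagged after refits. None of these is the plan's own abandonment rate: they depend on assumed prevalences (with covariates simulated as independent in some of the runs), on the test form and on the refit sequence, and the plan sets no limit on refits. The opposite error matters as much: roughly 40% to 70% of accepted sets at an assumed 0.5 SD difference exceed 0.25 on some covariate, a threshold that is itself conventional.

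The harm is mainly to the comparative superiority claim, which would be lost or less credible. It is not mainly a loss of power: against 56%, power is near 100% at the planned 16.6% and falls short (69% versus 81%) only at the 0.434 reference rate. Separately, and from the text alone, sections 10.6.3 and 10.6.4 give different triggers for the same fallback.

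**What to change.** Amend sections 10.6.3 and 10.6.4 before the propensity analysis is run:

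1. Judge balance by the stratum-weighted standardised difference of each covariate against a limit fixed in advance, for example every absolute value at or below 0.25, assessed by the same outcome-blind statistician.
2. Report the F and chi-square tests as description only, naming the chi-square form.
3. Fix the order and maximum number of refits.
4. State one trigger for the 56% goal that covers both remaining imbalance and inadequate stratum coverage, and use it in both sections.

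In simulation series A, a 0.25 limit accepted 99.8%, 91% and 57% of data sets at true differences of 0, 0.3 and 0.5 SD, so acceptance falls as imbalance grows, as it should. The cost is SAP wording only: no new data, patients or visits. The limit is a convention, so it must be set in advance; chosen afterwards, it would no longer be pre-specified.
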